Demographics: Basic demographic information will be collected for all participants. Information collected will include age, race/ethnicity, sex, gender identity, marital status, level of school, primary disability, use of a mobility device, and living arrangement.

Bayliss Comorbid Conditions: The Bayliss is a multimorbidity scale that assesses the impact of different conditions on daily activities as a measure of disease severity, conceptualized as self-reported disease burden. This scale was designed in order to create a subjective measure of comorbidity, to be used especially in studies using QoL outcomes, where the patient's perception plays an important role.¹¹⁸⁻¹²⁰

Process Evaluation

Reach. Enrollment and retention will be tracked by the research coordinator using REDCap, an online data entry program. Recruitment information for each participant will include the potential participant's initials, gender, birthdate, race, zip code. Reasons for denying participation in the study as well as study attrition will also be tracked via REDCap.

Fidelity. In order to guarantee treatment fidelity, or our ability to provide the same treatment as planned to each participant, we will use a Session by Session checklist following similar methods of Weersing et al.¹⁴⁵ This grid specifically outlines the pre-, during, and post-treatment visit requirements for each treatment session. It is designed to be a checklist in which therapists check off the action once it is completed. During weekly interventionist meetings, the lead therapist will review the treatment grid for each participant to guarantee the necessary components of the intervention are being delivered. A fidelity checklist designed to assess therapist adherence and competence in delivering the treatment intervention will also be used.¹⁴⁶

Dose. In order to effectively measure the dose of treatment provided for each participant, we will measure both the dose that was delivered to each person (minutes of each treatment session and number of session) as well as the dose received (recommendations implemented/total recommendations). We will use a spreadsheet or Time Log to track minutes spent in each treatment session and another spreadsheet or Prescription Log to track the recommendations made and implemented for each participant.

Adherence. Adherence measures the participant's continued use of the implemented modifications. We will use the standardized approach of Cumming et al.¹⁴⁷ to calculate adherence as recommendations used/total recommendations. Interventionists will rate adherence with intervention at the final session by using the Prescription Log to track recommendations made, implemented and reasons that any recommendations were not implemented. Initial adherence will be a proportion of the number of recommendations implemented /recommendations suggested. Finally, we will determine the number of recommendations used/recommendations suggested at 6 months. Reasons for abandoning strategies will be examined using the Adherence Log, in which the participant will report on current level of use for each modification: very useful, somewhat useful, not at all useful, no longer use equipment. Any independence that was regained by improved sensorimotor performance will not count against the adherence rating.

Cost. The cost of the treatment will be measured by tracking cost of modifications and adaptive equipment for each participant. This will be tracked using the Invoice Form which includes both costs from the contractor as well as costs of any equipment ordered from a medical supply company or obtained from a community resource (medical equipment lending program). The total amount of money spent on each person will be tracked on this form.

Safety. To explore the safety of our study, we will measure the number of falls and the circumstances surrounding the falls with a self-report Fall Form used at the 6 month follow up visit. The rate and severity of the falls will be calculated using a standardized algorithm established by Tinetti, et al, 1988.¹⁴⁸ We will also track health care utilization for participants in both groups (# of emergency room and outpatient visits, # of hospitalizations, and number of days in therapy) using the Health Care Utilization Form.

Process Evaluation

The components and data sources of the process evaluation are presented in Table 4. We will conduct a process evaluation to understand the feasibility and to refine the components of the intervention in preparation for a definitive trial.¹⁶² We will monitor recruitment metrics for all eligible participants including demographic characteristics, enrollment status, and reason for decline. We will determine the fidelity of the intervention by determining whether the intervention was delivered as planned and calculating the dose of the intervention received by both groups (number of minutes and number of sessions delivered). Interventionists will rate adherence at last visit as the number of recommendations implemented per recommendations suggested.¹⁶³ Long-term adherence will be calculated as the number of recommendations used at 6 months per recommendations suggested. We will examine reasons for abandonment of strategies. Environmental modifications are not provided as part of standard care in the United States; therefore, reliable cost data are not available. We will track the cost of service provision (in the treatment group) to prepare for future cost-effectiveness studies. We will record occupational therapist time to provide services (direct and indirect). The hourly wage of the contractor will be estimated using wage rates for the St. Louis area as reported by the US Bureau of Labor Statistics.¹⁶⁴ All materials costs will be captured from invoices. Costs will be estimated from the payer perspective (eg, Medicare allowable will be used to estimate covered clinical encounters.)¹⁶⁵

Table 4. Process Evaluation Construct Data: Source and Form

Reach	Enrollment; retention*	Reason eligible not enrolled; recruitment rate; retention rate
Fidelity	Implemented per plan [^]	Session by session checklist of each component
	Dose delivered [^]	Minutes of treatment at each session; number of sessions
	Dose received [^]	Recommendations implemented/total recommendations
Adherence	Adherence to recommendations ⁺	Recommendations used/total recommendations at 6 months; cause of abandonment
Costs	Costs [^]	Final prescription and invoice (materials); treatment grid (time)

Notes: Data source *Recruitment coordinator; [^]Interventionist notes; ⁺ 6- and 12-month follow-up assessment.

Statistical Analyses

First, we will examine the distributional characteristics of study variables (outcomes, covariates). Basic descriptive statistics for each measure and the intercorrelations among study variables will provide a simple initial view of the sample characteristics (demographic and health-related variables). Second, we will determine whether participants are representative of the eligible population by comparing baseline sociodemographic characteristics (eg, age, gender, education) of the study population with those eligible to participate in the study but who declined to participate. Continuous variables will be analyzed with the appropriate parametric methods (eg, *t* test) to test for differences between the participants in the study and those who refused. Discrete variables will be analyzed with the appropriate nonparametric test (eg, chi-square test of association) to test for differences between the participants in the study and those who refused.

Next, we will use unpaired *t* tests and chi-square tests to compare baseline characteristics in the 2 groups for descriptive information (except when statistical assumptions are not met, in which case we may use Wilcoxon or Fisher exact tests). We will examine the process data before the efficacy analyses.¹⁷⁰ The goal of Aim 1 is to examine the feasibility of conducting a larger trial by conducting a process evaluation. We will conduct between-group comparisons of process end points collected at 6 months (eg, health care utilization rate, safety, dosage delivered, and adherence rate) using unpaired *t* tests or chi-square tests. We will compare the characteristics of patients that complete the assigned intervention to those who do not for differences in disability severity and comorbidities. Descriptive statistics will be used for costs per participant and adherence.

The goal of Aim 2 is to test the hypothesis that the adapted program will result in greater improvements in participation and daily activity performance than control at 6 months after intervention. Mixed-model repeated-measures analysis of variance will be used for longitudinal analyses of variables measured at >2 time points (ie, Reintegration to Normal Living Index, I-HOPE). The focus of this analysis will be the significance of the interaction between group and time. Hypotheses will test for interactions in terms of the equality of changes over time in the 2 groups. Contrasts will be used in testing the null hypothesis that changes between 2 specific time points in one group are equal to corresponding changes in the group. I-HOPE scores will be analyzed with analysis of covariance with the 6-month value as the dependent variable and the baseline value as the covariate. For all analyses, we will determine whether required distributional and model-specific assumptions are satisfied. To explore the potential trial end points, we will select the best independent indicator of participation and compare the measures for sensitivity and statistical efficiency with data collected at 6 months after intervention.

Sample Size Calculations

Although statistical significance is not the goal of this study, we estimated a sample size using a power analysis for a 2-sided, 2-sample, unequal-variance *t* test using G*Power with a significance level of 5% and power of 80%.¹⁷³ The sample size calculation includes a correlation between baseline and follow-up measures and is based on analysis of change scores, which is equivalent in efficiency to the proposed analytic model. Data were used from a pilot study with a total of 113 community-dwelling older adults.¹⁰⁰ We estimated the sample size for the mechanism of action (reducing environmental barriers). Environmental barrier mean changes in intervention and control groups were 26.28 (SD 18.03) and 10.09 (SD 22.27), respectively. A sample size of 50 (25 in each group) is needed to provide 80% power.

Potential Benefits, Risks and Alternatives

Benefits

All participants will receive a baseline assessment provided by a registered and licensed occupational therapist. In addition, all participants will receive the intervention at no cost. Participants will receive \$5 for each month that falls are reported (waitlist control will receive the intervention after the 6 month follow-up is completed). Participants that participate in the COVID-19 pandemic survey will be entered to win a \$50 gift card for each survey that is completed.

Risks

Potential risks of research participation (physical, psychological, financial and legal risks among others) are considered minimal in all the projects (45 CFR46.404). Minimal risk may be involved as the general data collection procedures involve participant interviews and questionnaires that are time consuming (for participants receiving the intervention, 90 minutes for the initial home assessment with follow-up visits at 6 months) and may result in fatigue or aggravation. In addition, some questions may touch on emotionally sensitive issues that could cause anxiety or other forms of emotional stress. The performance-based testing (I-HOPE) involves observation of everyday activities that may result in fatigue or embarrassment. Participants will be informed that their involvement in this research study is voluntary and that they may choose not to participate or withdraw their consent at any time. Withdrawal from the study will not affect the commitment of the community agency to administer care, and there will be no penalty or loss of benefits to which participants are otherwise entitled. Participants who undergo the study visits will be given the option to reschedule the visit

or take a break at any time during the study if necessary. All research-related information will be kept confidential and accessible only to authorized members of the research team.

Minimization of Risks and Confidentiality

Training and Compliance. All study personnel involved in the conduct of this research will receive the required education on the protection of human research participants prior to the funding of this project in accordance with the NIH policy. We are a HIPAA-covered entity and comply with all HIPAA regulations. To protect against and minimize potential risks, participants will be carefully screened and evaluated.

Safety. To minimize the risk of a fall, participants will wear a gait belt during the in-home evaluation of performance. Participants will be trained in the use of all modifications by a licensed and registered OT. Participants (newly enrolled and those still receiving any in-person study-related visits will be asked their COVID vaccination status.

Minimize discomfort. To avoid or minimize symptoms of fatigue, agitation, or emotional distress due to testing, participants will be instructed to notify the rater or interventionist if they experience any discomfort. They will also be periodically questioned about their tolerance for the tests/intervention. Testing and interviews will be terminated if participants develop fatigue, agitation, or emotional distress.

Protect identifiers. An ID number will be assigned to each participant. All data collected from a participant will be labeled with the ID number. All participant electronic and hard-copy data will be kept under double-lock protection. All hard-copy forms that contain personal identifiers (e.g., name, address, phone numbers) will be stored in a separate locked file drawer under double-lock protection. No publication or presentation of the study data will uniquely identify or provide sufficient information to uniquely identify participants.

To guard against unauthorized data access, all shared-use computer systems at Washington University School of Medicine are protected with passwords, which are changed at four-month intervals. Only individuals with a particular "need to know" status are given access, and system privileges are carefully restricted. All personal computers are located within a secure area, and the system is locked when not in use.

For data entry (in the field or from paper forms), the Washington University Division of Biostatistics Informatics Core will be used as a central location for data processing. Washington University belongs to a consortium of institutional partners that work to maintain a software toolset and workflow methodology for electronic collection and management of research and clinical trial data. REDCap (Research Electronic Data Capture) data collection projects rely on a thorough study-specific data dictionary defined in an iterative self-documenting process by all members of the research team with planning assistance from the Division of Biostatistics Informatics Core. REDCap servers are securely housed in an on-site limited access data center managed by the Division of Biostatistics at Washington University. All web-based information transmission is encrypted. The data is all stored on a private, firewall protected network. All users are given individual user identification and passwords and their access is restricted on a role-specific basis. REDCap was developed specifically around HIPAA-Security guidelines and is implemented and maintained according to Washington University guidelines. All paper forms collected in the field with or without personal identifiers will be transported via locked brief cases.

SAS software package will be used for data analysis. Datasets generated from these programs will be password protected, which will make accessing study data difficult even in the event of unauthorized computer access occurs. Systems connected to the Ethernet are carefully controlled, and all systems without Ethernet access control are insulated from the backbone by bridges or routers. The Ethernet cable itself is routed only through secure passageways.

Adverse Event Reporting and Safety Monitoring

Because risk in the proposed study is considered minimal, the DSMB will meet semi-annually to review overall study progress, safety, and efficacy. However, if more frequent monitoring is required, it will be implemented accordingly. At the meetings, [name] will review progress of the data collection process, evaluate any unanticipated or anticipated effects of study participation, and monitor the integrity and the accuracy of the data generated from the study. [name] will present progress in the study and interim analyses at each meeting.

Minutes of each meeting will be reported to the HRPO. [name] will be responsible for executing recommendations made by the committee.

All serious adverse events will be reported to the HRPO in the following time frames: a) death, immediately; b) life-threatening, within seven calendar days; and c) all other SAEs, within 15 calendar days using the Electronic Serious Adverse Event Reporting System. Should there be a serious adverse event that occurs that increases the risks to the participants, the study will be stopped, an investigation will be conducted, and a findings report will be generated before the study is resumed.

Indemnity

Washington University School of Medicine is responsible for any non-negligent damage incurred as a result of participating in the trial. The indemnity is renewed on an annual basis. Washington University School of Medicine assures that it will continue renewal of the indemnity for the duration of the trial.

Ethics and Dissemination

This protocol and the template informed consent forms will be reviewed and approved by the Washington University institutional review board with respect to scientific content and compliance with applicable research and human subjects regulations. All study personnel involved in the conduct of this research will receive the required education on the protection of human research participant rights. Study projects will not begin until the IRB has reviewed and approved all study materials. The protocol will be updated as needed and submitted to the IRB for review.

On publication of the study results, participants will be invited to attend a community meeting during which the results of the study will be reported. The information will be repeated during three community sessions to be held during daylight hours. Participants will receive a mailing announcing the meetings and summarizing the study findings. The location of the meetings will be in a fully accessible auditorium with accessible parking and access to public transportation. A written report will be distributed, and the results will be presented by the study investigators, followed by a question-and-answer period. Refreshments will be served, and participants and their family members will be thanked for their generous support of the project.

Authorship Eligibility and Contributorship

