Study Type	Project 4 Testing preliminary efficacy of a program to reduce barriers to community participation. Translational Trial Phase I Allocation: Randomized Intervention model: Parallel Assignment Primary purpose: Community reintegration
Date of First Enrollment	November 3, 2020
Target Sample Size	50
Recruitment Status	Project 4, closed to recruitment
Primary Outcome(s)	
Project 4 Testing Preliminary Efficacy of a Program to Reduce Barriers to Community Participation: We will test the working hypothesis that an adapted program, focused on resolving environmental barriers and building self-management skills in the home and community, will be feasible and superior to usual care for daily activity performance and participation outcomes. The hypothesis is based on our previous work,^{2,3} the work of others,⁴⁻⁶ and our unpublished preliminary data.
 
Aim 1. Determine the acceptability and feasibility of the adapted program. We will conduct a process evaluation⁷ of this intervention to evaluate the acceptability and feasibility and to aid in the interpretability of the trial. We will test the hypothesis that the adapted program will have high acceptability (80% retention), high fidelity by therapists (95% of elements and 90% of dose delivered), low safety risk (no increased rate of falls or health care use compared with control group), and high adherence (80% of modifications in use) at 6 months.
 
Aim 2. Estimate the magnitude of efficacy of the adapted program on the primary outcome of community participation (RNL) and on exploratory outcomes of daily activity performance and self-efficacy (I-HOPE) to select optimal end points for a large pragmatic trial. We will test the hypotheses that the adapted program is superior to usual care at 6 months on the primary and secondary end points.
 
Time Points of Interest: Baseline, 1 month

ORGANIZATIONAL STRUCTURE AND RESPONSIBILITIES

Principal Investigator:

[name], OTR/L

Responsibilities include: Managing the operations of the study, ensuring tasks are completed, ensuring compliance with quality-assurance requirements (e.g., human participant protection), preparing interim reports, and publication of study reports.

Study Coordinators:

[name], MSOT, OTR/L and [name], OTD, OTR/L

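### Aim 1 states hypotheses against fixed feasibility benchmarks, but the Aim 1 analysis contains nothing that assesses a benchmark or its uncertainty

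*Combined protocol and SAP*

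**What the plan says.** The Primary Outcome(s) entry sets out Aim 1 as hypotheses to be tested: "We will test the hypothesis that the adapted program will have high acceptability (80% retention), high fidelity by therapists". The fidelity targets are "95% of elements and 90% of dose delivered", and the adherence target is "high adherence (80% of modifications in use) at 6 months". A further criterion is comparative, not a fixed value: "low safety risk (no increased rate of falls or health care use compared with control group".

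The Aim 1 paragraph of Statistical Analyses says: "We will conduct between-group comparisons of process end points collected at 6 months". The examples and methods follow: "eg, health care utilization rate, safety, dosage delivered, and adherence rate) using unpaired *t* tests or chi-square tests". It adds: "We will compare the characteristics of patients that complete the assigned intervention to those who do not". It closes with: "Descriptive statistics will be used for costs per participant and adherence". Adherence therefore appears in one paragraph both as a between-group test and as descriptive only.

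Three other places matter. Under Waitlist Attentional Control Treatment, controls have time-matched interview visits and are offered the program only after the 6-month follow-up. The Process Evaluation text with Table 4 counts long-term adherence per recommendation suggested, and counts minutes and sessions in both groups. Sample Size Calculations derives the total of 50 from change in environmental barriers, and says that statistical significance is not the study's goal.

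**The concern.** Whether retention reaches 80%, or delivered elements reach 95%, is a question about one quantity and a fixed value. A comparison of two arms does not answer it: if both arms retained 65%, a between-group test would show no difference, yet the target would be missed. Descriptive statistics give the percentage but, as written, no interval. The documents contain no one-sample test, confidence interval, precision statement or reading rule for any of the four fixed benchmarks.

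For adherence the planned test is also misplaced, because at 6 months the control group has no program recommendations to use or abandon.

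At stake is the feasibility conclusion. The process evaluation is meant to prepare for a definitive trial. A percentage near its target, reported with no indication of how far it could lie from the truth, would carry more weight into that decision than 25 to 50 people can support.

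**Working it through.** **1. The plan's own figure.** The only sample size calculation concerns environmental-barrier change: means 26.28 (SD 18.03) and 10.09 (SD 22.27), two-sided 5%, power 80%.

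- Difference: 26.28 − 10.09 = 16.19.
- Pooled SD: √[(18.03² + 22.27²)/2] = 20.26.
- n per arm: 2 × (1.960 + 0.842)² × (20.26/16.19)² ≈ 24.6, so 25 per arm and 50 in total.

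The stated 50 reproduces. A Welch calculation with the noncentral t gives 26 per arm, which is close enough. No Aim 1 benchmark enters this calculation, so the precision of the benchmarks has to be worked out separately.

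**2. Each Aim 1 criterion beside its planned analysis.**

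| Criterion | Target | What Statistical Analyses provides | Assesses the target? |
|---|---|---|---|
| Retention | 80% | not named among the between-group examples | no |
| Elements delivered | 95% | not named among the between-group examples | no |
| Dose delivered | 90% | between-group test | no; it compares contact in the two arms |
| Modifications in use at 6 months | 80% | between-group test and descriptive | no; controls have no value |
| Falls, health care use | no increase over control | between-group test | comparative, so the design of the analysis suits it |

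**3. Precision of retention.** The unit is the person, so exact binomial (Clopper-Pearson) limits apply directly. The denominator is 50 if both arms count and 25 if only the treated arm does. With retention exactly on target:

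- 40/50: 95% CI 66.3% to 90.0%.
- 20/25: 95% CI 59.3% to 93.2%.

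**4. Consequence if the point estimate alone were read against 80%.** This reading rule is an assumption, and the true rates are chosen for illustration. The chance of an observed value of at least 80% is P(X ≥ 40 | n=50, p) or P(X ≥ 20 | n=25, p):

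| True retention | n=50 | n=25 |
|---|---|---|
| 70% | 8% | 19% |
| 75% | 26% | 38% |
| 80% | 58% | 62% |
| 85% | 88% | 84% |

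So a true 75% would seem to reach the target in 26% or 38% of trials, and a true 85% would seem to miss it in 12% or 16%.

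**5. Adherence.** Recommendations are nested within about 25 treated people. The documents give neither the number per person nor the within-person correlation (ICC). As an illustration, assume 10 recommendations each, 80% in use, and an ICC of 0 to 0.5. The half-width is 1.96 × √[0.16 × (1 + 9 × ICC)/250]:

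- ICC 0: 5.0 points.
- ICC 0.1: 6.8 points.
- ICC 0.3: 9.5 points.
- ICC 0.5: 11.6 points.

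The same issue arises for elements and sessions, but the counts needed to put figures on them are not given.

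**6. Would a formal test be better?** An exact one-sided 5% test (my choice of level) of retention against 80% needs 45/50 or 24/25. Its power at a true 90% is 62% or 27%. The trial is too small for such a test to be useful, which points to estimation with intervals.

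**The case against.** The strongest reply is that this is a pilot. The sample size section disclaims statistical significance, and the process evaluation is meant to show feasibility and refine the program. On that view the benchmarks are descriptive targets and no test is owed. This stands as far as formal testing goes, and it is why the remedy is estimation. It does not remove the gap, because the aim is worded as hypotheses to be tested and an estimate still needs its uncertainty.

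Four stronger readings are tempting, and the documents do not support them.

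- A reader might infer that a program below its benchmarks will be declared feasible on bare point estimates. No rule for declaring feasibility is given, lenient or otherwise. Step 4 is conditional on an assumed rule, and near-even odds at the threshold itself are a property of almost any cut-off.
- A reader might infer that the only planned tests compare the two arms. Statistical Analyses also compares participants with decliners and completers with non-completers, although neither bears on a benchmark.
- A reader might infer that dose exists only in the treated arm and that its between-group comparison should go. Controls have time-matched visits, and minutes and sessions are counted in both groups, so that comparison is a legitimate check on equal attention.
- A reader might infer that recommendations will be pooled as if independent. Nothing says so; the analysis unit is simply not stated.

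**Conclusion.** The point holds as a gap in the analysis plan. Four fixed benchmarks are called hypotheses, and no planned analysis assesses any of them or its uncertainty. Separately, the between-group test of 6-month adherence cannot be interpreted, and it conflicts with the descriptive treatment of adherence in the same paragraph.

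The size is firm for retention: an interval of 66% to 90% at 40/50, or 59% to 93% at 20/25. The 26% and 38% figures rest on an assumed point-estimate reading and a chosen true rate of 75%. The adherence half-widths rest on an assumed 10 recommendations per person and an assumed ICC range, so they are illustrative only. The comparative safety criterion is outside this point.

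Nor does the finding justify a demand that the lower confidence limit clear the benchmark. For retention that would need 46/50 or 25/25, and a true rate of 90% would satisfy it only 43% of the time at n=50 and 7% at n=25 (0.90²⁵ = 0.07). For a pilot this is a worthwhile correction and does not undermine the design.

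**What to change.** In the Aim 1 paragraph of Statistical Analyses:

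1. Delete the between-group test of adherence and keep adherence as a treated-arm estimate.
2. Report each fixed benchmark as a one-sample estimate with a 95% confidence interval beside its target. For retention, use the exact binomial interval and state whether the denominator is the treated arm or all randomized participants.
3. For element fidelity, program dose delivered and adherence, summarize within each treated participant first, then form the interval across participants so that clustering is respected (for example, a bootstrap over participants). Name a fallback for ceiling data, because a bootstrap has zero width if all 25 people score 100%. One option is the exact lower limit for the share of participants with full delivery. At 25/25 it is 86.3%, and it is also a conservative lower limit for the mean, since the mean cannot be below that share.
4. Keep the between-group comparisons of safety, health care use and contact dose (minutes and sessions in both groups).
5. Word the feasibility conclusion from the estimate and its interval, not as a bare statement that the target was met, and do not require the lower limit to exceed the benchmark.

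The cost is a few lines of plan text and code. No new data or change in conduct is needed, which matters because recruitment is closed. The downside is that some benchmarks will carry wide intervals and less definite conclusions.
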